The study is an individually randomized group treatment (IRGT)³⁴ trial such that the individual, in this case the family, is the unit of randomization. It differs from a classic individually randomized trial in that the intervention is either a group intervention or conducted by an agent responsible for implementing the intervention in a defined set of individuals. The PLAN study will evaluate the effectiveness of family based treatment (FBT) delivered by a coach versus usual care (UC) treatment delivered by primary care providers. Both FBT and UC will be delivered in pediatric offices. In PLAN, participants are randomized at the family level and only one eligible child (the index child) is included in the primary outcome analysis. The trial will enroll up to 1284 subjects from 528 randomized families at four sites, each having at least one overweight/obese participating child age 6-12 and at least one participating parent. Since the study

has four sites with three coaches per site, the analysis plan involves a nesting of the coach within the site. Some sites have backup and floating coaches that are involved in delivering FBT to study participants, which will also be accounted for when outcome data is analyzed (**This change was made on 12.4.18 prior to review and approval by the DSMB, DSMB approved protocol addenda on 11.18.19**). While this nesting suggests a classic cluster randomized trial, an IRGT trial is different because the nesting applies only to the intervention group. Since the UC group has no nesting factor in this IRGT trial, a proper analysis must reflect the fact that the FBT group and the UC group must use different covariance structures. In addition to one participating child and parent from each family, the sample will also include up to 228 overweight/obese siblings and non-participating parents who will not be direct recipients of the intervention. There will be two years of follow-up with comprehensive assessments at baseline, 6, 12, 18 and 24 months. The primary outcome is percent over BMI at 24 months in the child. Our primary hypothesis is that the FBT intervention will be superior to UC alone in the participating child (**DSMB approved protocol addenda, 11.2.18**).

[figure not shown]
Outcome and Objectives

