Participating parent and child weight will be measured at each major assessment (at baseline and every 6 months), and weight will be assessed throughout FBT as part of a goal setting and reinforcement system by the blind assessors. *Child height will also be measured at each major assessment or as needed to determine progress (This change was made on 11.9.17 prior to review and approval by the DSMB, DSMB approved protocol addenda on 11.2.18)*. Weight will be measured using a wireless, portable scale (SR Scales, Tonawanda NY), calibration certified. Two weights for each participant will be taken according to a uniform protocol and will be written on hard copy measurement sheets. The handwritten weights will be manually entered into the REDCap database by a blinded measurement coach, which will

eliminate potential measurement bias and minimize errors in data entry (*DSMB approved change, 11.18.19*). Height will be measured using the portable stadiometer HM200P PortStad by the Charder manufacturing company within the pediatric practices (This change was made on 4.6.17 prior to review and approval by the DSMB, DSMB approved protocol addenda on 11.2.18). Hard copy height and weight measurement forms will be uploaded to the secure REDCap database to allow the CCC, DCC and TFC to check for transcription and/or unit of measurement errors. All assessors will be provided with the height and weight protocol (see Height and Weight Measurement in **Appendix C**) in order to ensure that participants are being measured accurately and consistently and we will retain the written record of participant height and weight, as well. On the basis of height and weight, BMI is calculated according to the following formula: $BMI = kg/m^2$. Children will be considered overweight at or above the 85th BMI percentile for their age and sex.³⁵ Parents will be considered overweight if their BMI is greater than or equal to 25 kg/m^2 , and obese if their BMI is greater than or equal to 30.³⁶

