Families who are eligible for the study will meet with a trained study staff member and will be given written and verbal information about the study. Full disclosure of the purpose of the study, the benefits and risks to individuals who participate, and the confidential nature of information obtained during the study will be explained to participants. Families will be aware from the onset that they will be randomly assigned to an active treatment condition (FBT) or a Usual Care (UC) control condition following baseline questionnaire completion. They will also be aware that their expected participation will be 2 years and may require anywhere from 26 sessions to 96 sessions of FBT if randomized to that condition. The study staff member will answer any questions the family has about the study, and then participants will be consented according to the policies and procedures of the University at Buffalo Institutional Review Board (IRB), the IRB of Record for the study. Study staff will follow-up with families by phone to inform them of their randomization status and will schedule the first FBT visit for those families randomized to FBT. PLAN coaches will also send reminders for FBT visits to their families throughout the study to decrease missed appointments.

2. Follow-up

Following baseline, families will be assessed at months 6, 12, 18, and 24. Links to brief self-report questionnaires via REDCap will be sent by study staff to all randomized families to complete prior to their assessment time point and families will be scheduled for assessment visits to collect height and weight measures and to complete the delay discounting task (DD; at 12 and 24 months only). Families will be greeted by the blinded PLAN coach or assessor at the practices to complete the DD computer task and collect heights and weights according to the protocols. Families will also have the opportunity to complete the REDCap questionnaires if they were unable to do so prior to the in-person assessment. Blinded PLAN coaches and assessors will complete all necessary forms and submit them into REDCap following this appointment. Families will be reminded of their next assessment in the series until it is the final visit. Home visits can be arranged for assessment appointments if necessary, and will be attended by two PLAN staff members.

3. Final Study Visit

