The DCC will organize annual site visits to all clinics that will focus on a detailed review of study procedures. Special additional site visits may occur if routine quality control measures determine that a clinic is having difficulty with some aspect of the protocol. Site visitors will prepare an agenda that will include observations of the performance of study procedures and of the filing system that is used to store completed data forms. They will confirm that data forms are correctly filed, that IRB approvals are available, and that changes on forms are appropriately initialed and dated by the person who made the changes. In addition, site visitors may do random data audits in accordance with section **X.F.2**. Site visits will generally be conducted by a DCC staff person and by an investigator from another clinic.

III. Statistical Considerations

A. Statistical Analysis Plan

Data will be analyzed with SAS using the intention-to-treat principle. P-values less than 0.05 will be considered significant and all tests are two-sided. Details of how the intention-to-treat principle will be implemented are contained in a later section.

B. Primary Analysis

The primary goal of this study is to determine whether the change in weight status among children who have overweight/obesity (*Primary Specific Aim 1, DSMB approved protocol addenda, 11.2.18*) is superior among those who are randomized to family-based treatment (FBT) as compared to those who are randomized to usual care (UC) when treated in a primary care setting. The primary outcome measure in children is the percent over the age- and sex-specific 50th BMI percentile. The specific question of interest in the primary analysis is whether the change from baseline to 24 months in the intervention group is greater in the FBT group than in the UC group.

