In order to mask assessment of outcome measures,-all sites have implemented blinded measurement coaches that complete assessments and AE data collection, so that the PLAN coaches can focus on treatment. Coaches will remain blinded to group assignment outside of their caseload (This change was made on 2.28.18 prior to review and approval by the DSMB, DSMB approved protocol addenda on 11.2.18). To further ensure blinding, families will be notified that the assessor is unaware of their group assignment and will be asked not to discuss the frequency of them coming in to the practice, their group assignment, or the coach they normally see (DSMB approved protocol addenda, 3.18.19).

Although not possible to guarantee that coaches are blind to condition for families that are not in their caseload due to the families not being blinded, use of a standard protocol (see **Appendix C**) ensures objective and reliable measurement of the primary outcome. Assessors will be blind to prior heights/weights, further protecting against assessment bias.

Reducing Bias in Unmasked Groups

We recognize that there are numerous ways that the PLAN coaches or pediatricians can treat FBT UC families differently. We have several approaches to reduce bias. We are able to standardize interactions with PLAN coaches through extensive training, supervision and fidelity checks, which can help reduce bias from the PLAN coaches. Part of the training will include instructions not to state or imply that FBT may be better than usual care. We will not be directly training or assessing fidelity for usual care, as that would deviate from the reason for using UC as the control condition. However, we will be collecting information on usual care practices from participating providers at baseline and 24 months via REDCap surveys. Group assignment will not be in the families' charts, and unless a family directly says something to the pediatrician, the pediatrician may be unaware of group assignment.

II. Study Administration

Study Website

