a. “We will mail a standardized scale and [item(s)] to your address for the assessment. Please confirm your mailing address and any special delivery instructions for your residence.”

2. Contact PC to coordinate delivery of materials

f. Schedule the family’s remote measurement

i. “To allow time for materials to arrive for the measurement, we will schedule 2 weeks out from this call.”

ii. Give 2-3 possible days/times to schedule appointment.

g. Complete AE survey according to protocol

i. “At this time I have a 5-10 minute survey to go through with you. Is now a good time to complete this?”

1. If yes, complete AE survey.
2. If no, “is there a convenient day/time where I can contact you to complete this survey?” or email it to the family

h. Notify family that necessary questionnaires will be emailed and should be completed before the measurement appointment through REDCap.

i. If family does not have computer/phone access with internet:

1. Surveys can be done over the phone BEFORE the appointment
 - a. AEQ, DDs, FNPA, 24M Parent/Child
2. Measurement instructions will be mailed to their address

ii. Send reminder email 1 day before assessment if questionnaires are not complete

- i. Check when family's next well child visit is to coordinate in person follow-up measurement at a convenient date and time
 - i. "In addition to the remote measurement, we will also schedule a follow-up measurement at the pediatric office. Does your child have an existing well-visit appointment that would be convenient for you to schedule this follow-up?"
 - ii. If not, schedule a follow-up appointment that will take place in the summer
- j. Ending the phone call
 - i. "Thank you so much for your time today, I will send you a 1 week and 1 day reminder prior to your assessment. Please contact me with any changes or questions in the meantime."
- 2. Record all assessment information into your site's specific tracking spreadsheet.
 - a. Add date and time, and all other necessary information, (UB Assessments - Tracking, WU, NCH, UR)
 - b. Include family's consent for audio/video recording
- 3. Contact a blinded measurement coach to run the assessment via video conference or phone.
 - a. For 24 month assessments, both the blinded assessor and the PLAN Coach should be present
- 4. Send video conference email link to family and assessor using <https://zoom.us/home?zcid=2478> or Webex
 - a. Set the duration as 30 min, or 60 min for a 24 month assessment.
 - b. Set a password.

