 - c. Attach Family Instructions for measurements
- 5. Email all the surveys to the family through REDCap (see next section)
- 6. Confirm assessment dates with family one week before and the day of the assessment
 - a. Include the call-in information and instruction sheet again.

Step 2: PLAN Coach Instructions for FORMS AND PAPERWORK COMPLETION

NOTE: For 6, 12, and 18 month assessments, all surveys should be completed by families BEFORE the assessment.

For 24 month assessments, surveys should be completed by families BEFORE the assessment, AND the PLAN Coach should attend the assessment to give FBT materials and finish payment AFTER the blinded assessor leaves the call.

- 1. For families doing 12- and 24-month assessments, have them complete the online questionnaires.
 - a. At 12 month assessments: Child DD Validation, Child DD, Parent DD.
 - b. At 24 month assessments: Child DD Validation, Child DD, Parent DD, FN & PA, and 24 Month for both Child and Parent.
 - c. For families with internet access, use REDCap to send the online surveys.

- i. In the family's REDCap record, click the circle that corresponds to the questionnaire that needs to be sent
 - ii. Under the "Survey Options" drop down menu, select "Compose Survey Invitation"
 - iii. Fill out the invitation form
 1. Send out immediately
 2. Check the box to enable reminders and choose to resend every 3 days with recurrence up to 5 times
 3. Make sure it is your email address the email will be from, and choose the participant's email address to where it will be sent
 4. Type in subject line: "PLAN with Families 12/24 month survey"
 5. Compose a message in the text box.
 - a. For example, "Hi [Name], Please click the link and complete the questionnaire, following the directions provided. If you have any questions, contact your PLAN coach at [phone number here]."
 - b. Be sure to clarify if that specific questionnaire needs to be filled out by the parent or the child
 - iv. Repeat for each questionnaire that needs to be completed
- d. For families who don't have access to internet
 - i. DD tasks, FNPA, and 24 Month Surveys can be done over the phone BEFORE the assessment
 - ii. Contact PC about mailing paper forms if necessary

2. If the family needs a re-assent, re-consent, or an addendum:
 - a. These will become forms in REDCap
 - b. You will send them just like you send the surveys BEFORE the assessment
 - c. In the subject line, use: "PLAN with Families Consent form for [Name of participant]"

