	
  Calculate BMI  Plot BMI on BMI growth chart  Make a weight category diagnosis using BMI percentile
	Define BMI and explain consequences of high BMI to families
	Perform a thorough physical examination
	
  Measure blood pressure  Order lab tests
	Take a family history, including:
	
  Obesity  Type 2 diabetes  Cardiovascular disease  Early deaths from heart disease or stroke
	Assess diet and physical activity behaviors
	
  Sugar-sweetened beverages  Servings of fruits and vegetables per day  Daily eating patterns (e.g., consumption of breakfast, portion sizes, family meals)  Frequency of fast food or restaurant eating  Amount of moderate to vigorous physical activity per day  Screen time
	Provide positive feedback for behavior(s) in optimal range
	
  Elicit response to feedback  Reflect/probe
	Provide neutral feedback for behavior(s) not in optimal range
	
  Elicit response to feedback  Reflect/probe
	Query which, if any, of the behaviors the family may be interested in changing or which might be easiest to change
	Agree on a target behavior
	Assess readiness to change
	Assess self-efficacy to change
	Collaborate possible next steps to change
	Develop and write a plan for change
	Summarize change plan and provide positive feedback

	Offer referral to a more intensive behavioral weight management intervention if necessary
	Agree to follow up within a certain amount of time (e.g., 6 months from today)

24 Month Survey – Parent (DSMB approved protocol addenda, 9.29.19).

Date: _____

1. Which site are you at? *this is required for branching logic for the next question*
 - a. Buffalo
 - b. Rochester
 - c. Columbus
 - d. St. Louis
2. Who was your most recent Coach? *list of each site's Coaches will appear with a "Don't Know" option *
3. Were you ever assigned another Coach?
 - a. Yes
 - b. No

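### The 24-month remote procedure has the PLAN coach present with the blinded assessor, without saying when the coach joins or in which arm, so the assessor blind is put at avoidable risk

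*Combined protocol and SAP*

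**What the plan says.** The Description of Study Design fixes the endpoint: "The primary outcome is percent over BMI at 24 months in the child". The 24-month height and weight are therefore the measurements that masking most needs to protect.

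The Remote assessments Protocol in Appendix C deals with the coach's presence in three places:

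- Step 1, item 3a: "For 24 month assessments, both the blinded assessor and the PLAN Coach should be present". Item 4 then has one conference link sent to the family and the assessor, with a 60-minute slot at 24 months instead of 30.
- Step 2, NOTE: "the PLAN Coach should attend the assessment to give FBT materials and finish payment AFTER the blinded assessor leaves the call".
- Step 2, item 4b: the coach sends the video link while the assessment is under way, but once the assessor has gone.

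Masking of Assessment Staff says that coaches stay blind outside their own caseload, and that families "will be asked not to discuss the frequency of them coming in to the practice, their group assignment, or the coach they normally see".

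Separately, the Assessments section says that "weight will be assessed throughout FBT as part of a goal setting and reinforcement system by the blind assessors".

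**The concern.** The masking section treats the identity of a family's usual coach as information the assessor should not have. The remote procedure then has a PLAN coach present with the assessor at the primary time point. The coach has no measurement task there; the stated purposes are materials, payment and the link, all of which come later. Early presence adds risk and no benefit.

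The assessor is not a passive recorder. Under Step 3 the assessor talks the family through the procedure, gives feedback, voices corrections and confirms the values. Under the family height instructions the assessor asks for two more readings when the first two differ by more than 0.3 cm. An assessor who has learned the arm could influence these steps without meaning to.

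The Assessments sentence raises a related question. Only FBT families are weighed during treatment, so an assessor who took those weights would know the arm.

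**Working it through.** **1. Does anything keep the coach off the call during measurement?** Item 3a has both people present. The Step 2 note and item 4b govern when the coach acts, not when the coach joins. No text has the coach join only after the assessor leaves, or stay silent or off camera. One link and a longer slot fit a shared call. A strictly sequential visit is also possible, but it is not written down.

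**2. Would the coach's presence reveal the arm?** There are two cases, and the documents do not say which applies.

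- Coach attends for FBT families only: attendance itself shows the arm. The mention of FBT materials points this way.
- Coach attends for both arms: attendance tells the assessor nothing. Familiarity might, since FBT families are told to expect 26 to 96 sessions (Family Consent). However, coaches also screen families before randomisation (Screening) and track the assessments of both arms (Participant Tracking), so usual-care families may know a coach too.

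**3. Does the coach rotation break the blind?** Taking coaches A, B, C as 1, 2, 3 in Masking of Assessment Staff, A's families have backup B and measurer C, B's have C and A, and C's have A and B. Backup and measurer always differ, so the written rotation is not the problem.

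**4. Who takes session weights?** In Session Structure, weighing opens the session with the PLAN coach, and the person weighing is not named. In Masking of Assessment Staff, coaches do not take outcome measurements on their own caseload, and blinded measurement coaches do assessments so that PLAN coaches can concentrate on treatment. The Assessments sentence does not fit this.

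**5. How many visits could be affected?** Inputs are the planned accrual in the DCVS milestones table: 56 (from 1 November 2017), 84 in each quarter of 2018, 82, and 54 (April to May 2019). The sum is 56 + 336 + 136 = 528, as stated. Add 24 months, assume even accrual within each period and visits on their target dates, and count those on or after an assumed remote start:

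- 16 March 2020: 528 − 56 − 84 × 74/90 = 402.9, or 76%.
- 7 May 2020: 528 − 140 − 84 × 36/91 = 354.8, or 67%.
- 19 May 2020: 528 − 140 − 84 × 48/91 = 343.7, or 65%.
- Uniform accrual from 1 November 2017 to 15 August 2019 (the end date under Randomization), 652 days: 517/652 = 79% for the March start and 453/652 = 69% for 19 May.

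The March date is attached to the added COVID adverse-event questions. The May dates are the DSMB and IRB approvals of the Coronavirus Addendum. None is stated as the start of remote measurement.

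**6. How sensitive is the outcome to height?** BMI varies as 1/h², so a height shift dh changes percent over BMI (PO) by about 2 × (dh/h) × (100 + PO), downward when the reading is taller. Assume h = 140 cm and PO = 30 to 60; neither is given in the documents.

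- dh = 0.3 cm: 2 × 0.3/140 × 130 = 0.56, and with 160, 0.69 points.
- dh = 1 cm: 1.86 to 2.29 points.

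The smallest difference in the power table is 5.3 points. If every remotely measured FBT child were shifted by 0.3 cm and no usual-care child were, the group difference would move by 0.56 × 0.65 = 0.36 to 0.69 × 0.79 = 0.55 points. This shows sensitivity only. The 0.3 cm is a tolerance between two readings, and 1 cm has no source in the documents.

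**The case against.** Read together, the three remote passages can describe an orderly handover: assessor first, coach second. Payment and the raffle are not arm-specific, and Step 1 is written for families generally, so attendance in both arms is plausible and would be uninformative. Assessors are blind to earlier heights and weights, a random subset of families repeats the remote height, and an in-person follow-up measurement is to be scheduled. The masking section already concedes that the blind cannot be guaranteed. Above all, the unblinded parent positions the child, marks the height and reads it out, so assessor masking was never full protection for remote data.

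Most of this stands as a limit on how far the point goes. It does not remove the point. The handover reading depends on a join time that is not written. The section on implementing the intention-to-treat principle does not mention the in-person follow-up, so it cannot be assumed to replace the remote value. Conceding that families may let the arm slip is no reason for the procedure to add a route of its own.

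A reader might infer that the blind cannot hold as written. The documents do not support that: presence reveals the arm only if it differs by arm or if familiarity shows. A reader might also infer from the Assessments section that blind assessors really do weigh families in treatment. The phrase is more likely a misplaced modifier that belongs with the major assessments, and the session and masking sections describe a different process.

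**Conclusion.** The point holds as an avoidable risk to assessor masking at the primary time point. Item 3a has the coach present with the assessor, and the related text delays the coach's tasks without stating when the coach joins or for which arm. This conflicts with asking families not to mention their usual coach. Masking still matters because the assessor guides, corrects, confirms and asks for repeats, but it protects a parent-taken measurement only in part.

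Roughly 65 to 79% of planned 24-month visits fall after an assumed remote start between 16 March and 19 May 2020. This is an upper bound on the affected share, given planned accrual and visits on target dates, because the number of visits done remotely is not given. The height figures are not an estimate of bias, and nothing in the documents shows that bias occurred. The Assessments sentence is a contradiction to reconcile, not proof of unblinding.

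**What to change.** Amend Step 1 item 3a, the Step 2 NOTE and Step 2 item 4b together, since changing one alone would create a new contradiction. Suggested rule: *The PLAN coach does not join the measurement call. After the blinded assessor has recorded height and weight and left, the coach contacts the family on a separate link or call for materials, payment and the video link. The same procedure applies in both arms.* Step 4 already has the measurement coach tell the PLAN coach that the assessment is complete, which can serve as the trigger.

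In the Assessments section, state who takes session weights and who takes outcome weights, consistent with Session Structure and Masking of Assessment Staff.

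The cost is revised wording and a second link or phone call per family, with no added visits. The change does not address the parent's own lack of blinding.
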